5.3 Other parameters

The following base line data will be asked, to demonstrate comparability of both study groups. The influence of these potentially confounding characteristics will be addressed in the analysis:

- gender
- weight
- length
- medical history
- house hold size
- daycare and kindergarten

CHAPTER 6. STUDY PROCEDURES AND ASSESSMENTS

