3.3 Duration of the study and milestones

The study will continue for a whole year, to cover all seasons, and multiple vaccine batches as supplied by Baxter Ltd. The duration of the study for each participant is approximately one month from vaccination.

Proposed timing of events (dependent on availability of study products and schedules of their delivery by RIVM). In case of vaccine batches to be studied run out of their period of approved use or pass their expiry date, the study may stop earlier.

year	month	activity / step
2014	APR	delivery of the appropriate batches in the study area
2014	APR	sending letters to parents of eligible children, from start weekly letters
2014	MAY	first inclusions
2014	JUN	first fully completed questionnaires
2015	APR	last letters sent
2015	MAY	last inclusions
2015	JUN	last completed questionnaires
2015	SEP	final draft study report
2015	OCT	study report

CHAPTER 4. SUBJECTS

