4.2 Inclusion criteria

- children 14 months old (age range 13-18 months; boundaries included) who receive the NeisVac-C® and MMR vaccination in one of the participating clinics according to the NIP

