6.3 Assessments / collection of data

6.3.1 Preregistration and registration

Upon receipt of the first letter parents may pre-register for the study by reporting their email address and scheduled vaccination date. At this date, Lareb will send them an email with a link enabling the parents to register for the study.

After vaccination, parents are given a flyer with information about the study, and how to sign-up for the study (web address and study specific access code).

The following data are requested.

- general data

1. are MenC and MMR vaccines administered both? If only one, or more than 2, vaccines were given, the child cannot further participate.
2. reporting code
3. date of vaccination
4. batch numbers of administered vaccines (to be recorded at baby clinic)
5. injection sites of administered vaccines (arm/leg/left/right) (to be recorded at baby clinic)
6. registration of email address. Per email address, only one child can participate. For more children in a household/family (twins, triplets,..) separate email addresses are required.
7. accept Lareb privacy rules yes/no. Only proceed if ticked: yes.

- data of reporting parent and child

1. confirm email address
2. child: date of birth
3. child: sex
4. child: height at time of vaccination
5. child: weight at time of vaccination
6. baby clinic: place and street address (choose from list).

- base line data

1. medical history, did your child have: ... (tick if applicable)
 - infections,
 - coughing/dyspnea,
 - skin rash,
 - hypersensitivity or allergy,
 - vomiting and/or diarrhea,
 - other: please specify ...,
 - none of the above.

- concomitant medication

1. Does your child use any medication: if yes: specify the medicine, dose, start date and stop date if applicable

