9.5 Comparability of study groups

Both study groups should be comparable for baseline characteristics and potential confounders, as defined in Chapter 5.

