9.6 Statistical methods for data analysis

The primary endpoint of the study, fever cases observed within 4 days after vaccination will be analyzed using logistic regression with vaccination groups ("old" / "new" product) and potential confounders as listed in 5.3 as explanatory factors, applying a log link in order to obtain relative risk estimates at the end. Relative risk and its 95% CI of occurrence of fever cases with the "new" and "old" NeisVac-C® product will be calculated from the regression model assessing a potential increase of fever reactions with the "new" product. If the upper limit of the 95% CI is below 1.5 then the "new" product is considered to be non-inferior to the old one as far as fever reaction is concerned.

The secondary endpoints will be analyzed similarly and descriptive without the non-inferiority considerations.

CHAPTER 10. SAFETY REPORTING

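### The covariate list that fixes the primary fever model omits calendar time of vaccination, which is collected; adding it is a cheap, low-severity improvement

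*Protocol*

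**What the plan says.** Section 9.6 specifies a log-link regression for fever within 4 days, with vaccine group and "potential confounders as listed in 5.3 as explanatory factors". Section 5.3 lists gender, weight, length, medical history, household size and daycare or kindergarten, and says "The influence of these potentially confounding characteristics will be addressed in the analysis". Section 9.5 relies on the same chapter for the balance check: "Both study groups should be comparable for baseline characteristics and potential confounders, as defined in Chapter 5".

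Neither age nor any form of calendar time is on the list. The data for both are requested at registration (section 6.3.1): "date of vaccination" and "child: date of birth". Section 3.3 gives the reason for the long recruitment period: "The study will continue for a whole year, to cover all seasons, and multiple vaccine batches as supplied by Baxter Ltd". Section 4.2 sets the age window: "children 14 months old (age range 13-18 months; boundaries included".

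The synopsis mentions potential confounders without naming them. Section 9.6 narrows this to the 5.3 list, and no other section adds to it.

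**The concern.** The protocol does not leave the covariates open for a later analysis plan. It closes the list by cross-reference, so an analysis plan that follows 9.6 would leave season out of the primary model, and 9.5 would not call for a comparison of season between the groups.

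Background febrile illness in toddlers plausibly varies over the year, and fever is the primary endpoint. Allocation is by clinic (section 8.2), entry is voluntary with an assumed 15-20% participation (section 8.3), and timing depends on product availability and delivery (section 3.3). If the two groups differed in when their children were vaccinated, the difference would pass into the fever risk ratio. The decision rests on whether the upper 95% limit lies below 1.5. An imbalance towards the high season in the new-product group would cost power. The opposite imbalance would make a false non-inferiority claim more likely.

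**Working it through.** No figure in the protocol depends on this point, so there is none to reproduce. The calculation below shows how large the effect could be.

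**Inputs from the protocol.** Reference fever risk 6% and 1215 children per group (section 9.2); margin RR 1.5 on the upper 95% limit (section 9.6).

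**Assumptions (not in the protocol).** Two seasons, with fever risk 8% in the high and 4% in the low season, which average to the protocol's 6%. Group B is split half and half. A share s of group A is vaccinated in the high season. A milder contrast of 7% vs 5% is the alternative. Clustering and the other covariates are ignored.

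**Formulas.**
- pA = s × hi + (1 − s) × lo, pB = 0.06, spurious RR = pA/pB.
- SE(log RR) = √[(1 − pA)/(1215 pA) + (1 − pB)/(1215 pB)].
- Power at true RR 1 = Φ[(ln 1.5 − ln RR)/SE − 1.96].
- False non-inferiority rate at true RR 1.5: the same expression with pA multiplied by 1.5.

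**No imbalance (s = 0.50).** SE = √(2 × 0.94/(0.06 × 1215)) = 0.1606. Power = Φ(0.4055/0.1606 − 1.96) = Φ(0.565) = 71%. False-claim rate 2.5%. The 71% is the starting point on the risk-ratio scale with 1215 per group. It differs from the 80% in section 9.2, but that is a separate matter.

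**How large a chance gap to expect.** If timing is independent between children, the SD of the between-group difference in high-season share is √(2 × 0.25/1215) = 0.0203, about 2.0 percentage points. A 10-point gap is 0.10/0.0203 = 4.9 SDs. If the variance is doubled for clustering, it is still 3.5 SDs.

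**Results.** The power column puts the imbalance against the new product (s above 0.50). The false-claim column puts the same gap in its favour (s below 0.50).

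| Seasonal risk | Gap | Spurious RR (against / in favour) | Power at RR 1 | False-claim rate at RR 1.5 |
|---|---|---|---|---|
| either | 0 | 1.00 | 71% | 2.5% |
| 8% vs 4% | 2 points (1 SD) | 1.013 / 0.987 | 69% | 3.1% |
| 8% vs 4% | 10 points | 1.067 / 0.933 | 58% | 6.8% |
| 7% vs 5% | 2 points (1 SD) | 1.007 / 0.993 | 70% | 2.8% |
| 7% vs 5% | 10 points | 1.033 / 0.967 | 65% | 4.2% |

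Worked line for 2 points at 8% vs 4%: pA = 0.52 × 0.08 + 0.48 × 0.04 = 0.0608; RR = 0.0608/0.06 = 1.013; SE = 0.1600; power = Φ((0.4055 − 0.0132)/0.1600 − 1.96) = Φ(0.491) = 69%.

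The rows with a gap are conditional on that gap occurring. They are not the operating characteristics of the design as planned.

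**The case against.** The strongest reply is that the design already balances season. Clinics are randomised to one product (section 8.2) and keep it for the study year (section 7.4). Letters go out weekly (section 3.3), about a month before each child's scheduled visit (section 4.4), so timing follows the child's age and not the product. Season varies within every clinic. Parents are not told which product was given (section 8.1), so there is no evident reason for them to volunteer in different seasons by product. Medical history, daycare and household size already capture part of the infectious background. This largely stands, and it is why the expected effect is small.

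A reader might infer from section 3.3 that one product could run out or expire first, leaving the groups in different seasons. The text says only that the study may stop earlier. It does not say that one group would continue without the other. Uneven supply or uptake is possible, but it is an inference.

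A reader might also take the 58% power or the 6.8% false-claim rate as what the plan risks through chance. Those figures need a 10-point gap, far outside chance variation under concurrent supply.

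Nor do the documents support giving age equal weight. The range is 13-18 months, vaccination is usually at 14 months, weight and length partly stand in for age, and nothing in the protocol indicates that fever risk differs across this range.

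Two parts of the reply do not stand. Medical history is taken at registration and cannot fully represent exposure to seasonal infection over the following days. And this is not just a detail left to the analysis plan, because 9.6 names a closed list.

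**Conclusion.** The point holds as a low-severity improvement. The primary model's adjustment set is fixed to a list without calendar time, although the date is collected and coverage of all seasons is a stated reason for the study's length. Under concurrent, clinic-randomised supply the likely cost is slight: with an assumed 8% vs 4% seasonal contrast, a one-SD gap gives a spurious RR of about 1.01, power of about 69% instead of 71%, or a false-claim rate of 3.1% instead of 2.5% in the other direction. Material bias would require clearly different enrolment over time between the products, which the protocol neither states nor rules out. The seasonal contrast is assumed throughout, since the protocol gives none. The omission does not invalidate the primary comparison.

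**What to change.** Add calendar time of vaccination to the list in 5.3, as quarter (three terms) or an annual harmonic (two terms). Section 9.6 then adjusts for it and 9.5 tabulates it per group, with no further change to either. Age at vaccination can be tabulated too and entered as one linear term, but this is optional.

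No new data are needed, and the text change is a line or two. The cost is two to four extra terms in a log-link model with about 0.06 × 2430 = 146 expected fever cases, which already carries the 5.3 covariates. Entering household size as a linear term would offset some of that. Naming the term in advance also avoids a disputable post hoc adjustment if the groups turn out to differ in timing.

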7.2 Description of route of administration and dosage

NeisVac-C® will be injected intramuscularly (one dose is 0,5 ml). MMR will be injected subcutaneously (one dose is 0,5 ml, after reconstitution).

Injection sites are not prescribed in this protocol. The baby clinic personnel is asked to follow their usual practice. Neither the various organisations of child health care, nor the National Immunisation Programme prescribe the injection sites.

After injection, baby clinic staff is asked to write down which vaccine is injected where, and which batch numbers were used. Parents are asked to enter these data into the questionnaires.

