8.2 Randomization and stratification

Central randomisation: baby clinics are randomly assigned to use either the old or the new NeisVac-C®. Shipments are done according to a distribution list, generated to randomly assign either batch to any participating baby clinic, to ensure that both groups are similar in size, and that local differences in confounding factors (e.g. concurrent infections, habits and attitudes towards vaccinations, ...etc) are balanced out.

RIVM/DVP will generate the distribution list, and will provide the baby clinics accordingly (Appendix 2).

8.3 Study size and recruitment population.

In order to evaluate 1215 children per group according to protocol (see paragraph 9.2) we need to recruit higher numbers of children. The following estimations are done to determine the population size to target for participation. With 1215 per group we need 2430 fully evaluable and complete datasets. We assume that 90% of data from an estimated 2700 respondents that have completed all questionnaires are evaluable. We assume that after starting the questionnaires 75% of responders will also complete the last questionnaire, thus giving an estimation of 3600 responding parents that start and agree to participation. Experience of RIVM indicates that about 40% of parents participate to a similar questionnaire proposal. However, to be sure to include the desired number of respondents we assume a lower percentage: 15-20%. Thus we assume that 18.000 to 24.000 parents need to be addressed for taking part in the investigation. In addition, to compensate for other interferences or loss, we intend to address 25.000 parents.

8.4 (Un) blinding procedure

Not applicable

CHAPTER 9. STATISTICS

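### Injection limb follows clinic practice and is recorded, but it is absent from the covariate list and the balance check, so local-reaction comparisons can carry an unseen chance arm/leg imbalance between clinics

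*Protocol*

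**What the plan says.** All references are to the protocol.

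- **Limb is not standardised.** Section 7.2: "Injection sites are not prescribed in this protocol. The baby clinic personnel is asked to follow their usual practice". No outside rule fills the gap: "Neither the various organisations of child health care, nor the National Immunisation Programme prescribe the injection sites".
- **The clinic is the unit of allocation.** Section 8.2: "baby clinics are randomly assigned to use either the old or the new NeisVac-C". No stratification factor is named. The section relies on the allocation to ensure "that local differences in confounding factors (e.g. concurrent infections, habits and attitudes towards vaccinations, ...etc) are balanced out".
- **Limb is collected.** Registration (6.3.1) asks for "injection sites of administered vaccines (arm/leg/left/right) (to be recorded at baby clinic"), and questionnaire 1 (6.3.2) locates each local reaction to a site.
- **Local reactions are a secondary endpoint.** Section 5.2 solicits them at the NeisVac-C site, the MMR site, or both.
- **The covariate list omits limb.** Section 5.3 names six characteristics and adds "The influence of these potentially confounding characteristics will be addressed in the analysis". Section 9.6 enters "potential confounders as listed in 5.3 as explanatory factors" in the fever model, then says "The secondary endpoints will be analyzed similarly and descriptive without the non-inferiority considerations".
- **The balance check omits limb.** Section 9.5 covers characteristics and confounders as defined in Chapter 5.
- **Section 9.4 reads differently.** It gives the secondary endpoints a descriptive analysis only.

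**The concern.** The study exists because a regulator asked how the reactogenicity of vaccine from the two production sites would be compared. Local reactions are part of that comparison. Whether a reaction occurs, or whether a parent notices it, may depend on whether the injection went into the arm or the leg.

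If limb is mainly a habit of the clinic's staff, its balance between groups depends on how many clinics are randomised rather than on how many children take part. One group can by chance hold more leg-injecting clinics. The crude risk ratio for local reactions then moves even if the two products are identical.

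None of the six listed characteristics stands in for limb, so a model built on them leaves the shift in place. Because the comparability check is drawn from the same chapter, a reader of the report would not learn that the groups differed. The limb is chosen before any reaction, so adjusting for it introduces no bias.

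**Working it through.** The protocol states no figure on this point, so there is none to reproduce. The text was checked first, then an illustrative size was worked out.

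**Text.** The sections agree on four facts: limb is left to usual practice (7.2), clinics are randomised (8.2), limb is recorded per vaccine (6.3.1), and limb is missing from the list (5.3). No section stratifies, adjusts or tabulates local reactions by limb.

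**A given imbalance.** Assume reaction risks of 20% and 30% in the two limbs, no product effect, and a 60/40 against 40/60 split:

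(0.6 × 0.30 + 0.4 × 0.20) / (0.4 × 0.30 + 0.6 × 0.20) = 0.26 / 0.24 = 1.083.

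**How large an imbalance chance can produce.** From the protocol: 1215 children per group (9.2). Assumed: K clinics, half to each product; each clinic uses one limb; half the clinics use the leg (p = 0.5); clinic-size coefficient of variation (CV) 0.6; limb risks of 20% v 30% or 22% v 27%.

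- SD of the difference in leg share between groups = √[4p(1−p)(1 + CV²)/K] = √(1.36/K).
- 95% limit of the shift in log risk ratio ≈ 1.96 × SD × (risk difference / mean risk). The last factor is 0.10/0.25 = 0.40, or 0.05/0.245 = 0.204.
- If each clinic mixes limbs 80/20, its leg share is 0.8 or 0.2 instead of 1 or 0. The spread is multiplied by 0.6, so the shift falls by 40%.

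| Clinics | 1.96 × SD | 20% v 30% | 22% v 27% | 20% v 30%, 80/20 mix | 22% v 27%, 80/20 mix |
|---|---|---|---|---|---|
| 60 | 0.295 | 0.118 | 0.060 | 0.071 | 0.036 |
| 120 | 0.209 | 0.083 | 0.043 | 0.050 | 0.026 |
| 200 | 0.162 | 0.065 | 0.033 | 0.039 | 0.020 |

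Simulating 5000 allocations per setting with one limb per clinic gives 0.115, 0.083 and 0.065 for 20% v 30%, and 0.060, 0.042 and 0.032 for 22% v 27%. The two methods agree. On the ratio scale, 0.032 to 0.115 is about 3% to 12%.

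**Against sampling error.** At 25% reactions and 1215 per group, with children treated as independent, SE(log RR) = √(2 × 0.75/0.25/1215) = 0.070 and the 95% half-width is 0.138. The shift is 0.032/0.138 = 0.23 to 0.115/0.138 = 0.83 of that.

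**Other assumptions.** Take 15% reactions in the reference limb, a limb risk ratio of 1.5, half the clinics using the leg, one limb per clinic and CV 0.5. The spurious risk ratio then has these 95% ranges, and an unadjusted 95% interval that ignores clinic excludes 1 this often, against a nominal 5%:

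| Clinics | 95% range of spurious RR | Interval excludes 1 |
|---|---|---|
| 50 | 0.88–1.13 | 12% |
| 100 | 0.92–1.09 | 8% |
| 400 | 0.96–1.04 | 6% |

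**The case against.** **The list is not closed for secondary endpoints.** In 9.6 the reference to 5.3 sits in the sentence on fever. For the secondary endpoints the text says only that they are handled similarly. The synopsis speaks of potential confounders without a list, and 9.3 allows for other confounders when defining the per-protocol set. Endpoint-specific covariates could be left to an analysis plan. This stands in part: it would be too strong to say that the protocol forbids adjusting for limb. But the only list it offers is the one in 5.3, the plain reading of 9.6 carries it over, and 9.5 confines the balance check to the same chapter.

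**The secondary analysis may be descriptive only.** Under 9.4 there may be no adjusted risk ratio to which limb could be added. That stands, and it changes the form of the remedy. It does not remove the problem, because crude proportions by group carry the same imbalance.

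**Randomisation deals with local habits.** Section 8.2 says so, and its examples are open-ended. Randomising clinics does remove systematic bias. It does not remove chance imbalance in the one allocation that is used. An interval that allowed for clinic would cover this variation, but it would neither correct the estimate nor show the imbalance.

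**One limb per clinic is the extreme case.** Section 7.2 speaks of personnel, so practice may vary within a clinic. This stands, and the 80/20 columns show the effect.

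A reader might infer that the local-reaction results will be biased, or that the fever conclusion is at risk. The documents support neither. The imbalance has mean zero, and the argument concerns injection-site outcomes, not the non-inferiority test or the sample size.

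**Conclusion.** The point holds as a limited one. A recorded variable, fixed before the outcome and closely tied to injection-site reactions, is left out of both the covariate list and the comparability check, while the design lets it vary by clinic. Local-reaction comparisons between the products can therefore reflect a chance arm/leg difference that nobody would see.

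The size is hypothetical. With 60 to 200 clinics, one limb per clinic and the assumed limb risks, the 95% limit of the shift is about 3% to 12% of the risk ratio, and about 40% less with an 80/20 mix. Many clinics, mixed practice or a weak limb effect would make it negligible; few clinics and a strong limb effect would make it larger. The protocol gives no clinic count, limb split or limb effect to decide between these.

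This is an improvement that costs almost nothing. It is not a flaw that threatens the study's main conclusion.

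**What to change.** 1. In 5.3 and 9.5, add the injection limb of each vaccine (arm, leg, unknown, from the registration data in 6.3.1) to the comparability table by group.
2. In 9.6, wherever a relative risk for local reactions is estimated, include the limb of the vaccine concerned as a covariate: NeisVac-C limb for NeisVac-C-site reactions, MMR limb for MMR-site reactions.
3. Reconcile 9.4 with 9.6 on whether secondary endpoints are modelled. If 9.4 governs, show local-reaction proportions by group within limb instead.
4. Leave the primary fever model unchanged.

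No new data are needed, and injection practice at the clinics is not affected. The cost is one extra parameter for limb in each local-reaction model and an unknown category for children whose site was not recorded.

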6.1 Schedule per eligible participant

time	actor	activity
- 4 wks	RIVM/DVP	sending letter to parents in region with predefined baby clinics. The letter is with headings of Lareb, and sent by actor.
-4 wks to-1 day	parents	pre-registration at Lareb LIM site, with contact details and planned date of vaccination
Day 1	baby clinic	
 - give MenC and MMR vaccinations - remind parents to the study described in the letter that parents received earlier. - record vaccinations on the study letter from the parents, and recording as usual for adequate registration by RIVM/DVP.
Day 4	parents	latest possibility to register for study, confirmation of date of vaccination
Day 5	Lareb	send questionnaire 1, reminder at day 7
Day 14	Lareb	send questionnaire 2, reminder at day 16
Day 28	Lareb	send questionnaire 3, reminder at day 32
Day 36	Lareb	closure

